#### EEG and Video Acquisition

EEG will be collected during the dose-charge titration session and during all treatment sessions to assess pre-ECT and pre-anesthetic baseline EEG recordings. An appropriately fitted 64-channel EEG Geodesics Sensor Net (Electrical Geodesics, Inc. Eugene, OR, USA) will be affixed to the scalp. Elefix electrode paste (Nihon Kohden America, Inc., Irvine, CA, USA) will be injected to maintain conductivity to the silver/silver-chloride electrodes. Electrode impedances on each channel will be optimized to be less than 100 kOhms/channel, per manufacturer's suggestions. Data (DC to 2000 Hz bandwidth 500 Hz sampling rate) will be acquired with a Net Amps 400 amplifier and Net Station version 5.0 and above (Electrical Geodesics, Inc.

12

Eugene, OR, USA) via a Late 2012 Mac Pro Workstation (Apple Cupertino, CA, USA). Whenever possible, video synchronized to EEG will be acquired using an Axis P3364LV network camera (Axis Communications, Lund, Sweden).

#### **2.4.7.1 Outcomes** (Further details on instruments are provided in appendices)

#### Primary and Secondary Outcomes

Primary outcomes include: the temporal recovery profiles for cognitive task performance, as measured using the Cognition assessment battery (Basner, Savitt et al. 2015); times for the return of responsiveness to auditory command; and the presence of delirium, evaluated through the 3-Minute Diagnostic Assessment for CAM-defined delirium (3D-CAM)(Marcantonio, Ngo et al. 2014).

Secondary outcome measures based on the EEG will include definitions of the seizures by standard techniques using both expert reader interpretation and quantitative techniques (Haider, Esteller et al. 2016). Central seizure duration will be visually determined by clinician evaluation of the frontal-mastoid bipolar EEG ictal complexes. Additional measures will be calculated from windowed analyses of the high-density EEG: power spectral measures of the interval between anesthetic induction to delivery of ECT stimulus charge; the seizure envelope for 1-12 Hz EEG power; peak-to-peak amplitude, calculated from the difference in maximum and minimum voltages within 300 millisecond time; periodicity of epileptiform discharges; inter-hemispheric symmetry of seizure discharges; intra- and inter-hemispheric coherence. When possible, these measures and power spectral estimates will be derived different phase of the ictal waveforms(Gerst, Enderie et al. 1982). The following postictal EEG measures will be assessed: duration of postictal EEG suppression; power spectral parameters flanking the return of responsiveness to verbal command; power spectral parameters from eyes open and closed epochs, including assessments of the posterior dominant rhythm. Spatiotemporal analyses will also focus on the propagation of EEG signatures during the ictal and early postictal period.

### 2.4.7.2 Data Collection

Outcomes, such as delirium assessments, will be entered into the Washington University School of Medicine Research Electronic Data Capture (REDCap) application. The baseline medications will be collected from the electronic medical record. The anesthetic and recovery record will be retrieved from the hospital's perioperative electronic medical record (Metavision by *i*MD*soft*®, Needham, MA). The cognitive assessments will be

completed using the COGNITION cognitive battery designed at the University of Pennsylvania(Basner, Savitt et al. 2015). The computer-based depression questionnaire will be completed through assessmentcenter.net developed by Northwestern University's Department of Medical Social Sciences. As standard care for tracking depression symptoms during an ECT course, treating psychiatry teams will administer the Quick Inventory of Depressive Symptomatology, Self-Report (16-Item), QIDS-SR16(Rush, Trivedi et al. 2003). To fully assess each patient's treatment response to ECT, the research team will use the electronic, as well as paper, medical records to access and record the following information for each treatment from the patients' entire ECT treatment course at Barnes-Jewish Hospital: QIDS scores, reason for treatment (diagnosis), the method of ECT (right-unilateral, bilateral, or bifrontal), treatment number, date of treatment, any medications including doses, charge/treatment parameters, central and peripheral seizure duration, any adverse events from the sessions, and any clinical notes regarding treatment efficacy or recovery from each procedure.

### 2.4.7.3 Optional Magnetic Resonance Imaging

In addition to the above procedures listed, patients will be given the option to undergo non-contrast magnetic resonance imaging (MRI). The MRI data will better allow interpretation of the EEG signals in relation to structural brain anatomy. The MRI scan will take place following completion of the patient's ECT treatment course at Barnes-Jewish Hospital. Structural MRI will be performed at the 10th floor West Pavilion Center for Clinical Imaging Research (CCIR). The MRI scan will use clinical sequences and will be read by board-certified neuroradiologist. The reading and images with be placed in the electronic medical record. Significant incidental findings will be disclosed to the patient and his/her physician. The patient will decide s(he) on disclose of Incidental findings of unclear clinical significance. Patients will be compensated \$50 for their time. There will be no charge to the patient for the MRI scan. If patients are unable to arrange transportation to/from Barnes-Jewish Hospital for pre-treatment testing, the study team will provide patients with such transportation through cab vouchers.

#### 2.5. Analytical and Statistical Methods

This is an exploratory study that seeks to track and characterize the reconstitution of consciousness and cognition following ECT coupled with general anesthesia. We hypothesize that the pattern (sequence and time

14

course) of reconstitution of consciousness and cognition following ECT with general anesthesia is different from general anesthesia alone. In particular, we propose that the cognitive and electroencephalographic features following ECT will be similar to those seen during postoperative delirium, which is a disorder of consciousness and cognition.

#### 2.5.1 Statistical Analysis

We will employ mixed-effects models to quantify trajectories of cognitive recovery over time while addressing inter-subject variance and missing data. Linear models with appropriate transformations will be used preferentially over non-linear models. Time and treatment intervention group will be included as fixed effects while random effects will account for repeated measures provided by each participant. Day of treatment relative to the dose-charge titration session will allow consideration of cumulative effects of treatment order that may remain biased despite randomization. To address differences in ECT-stimulation responsiveness, regression approaches will account for dose charge, central seizure duration, and age. Models will assess for the effects of treatment on the timing for the return of responsiveness to verbal command and the presence of delirium. Separate mixed-effects models will be generated to assess task performance in a group of young healthy volunteers during the recovery from isoflurane general anesthesia (Maier, McKinstry-Wu et al. 2017).

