# 2.3 Design and Participants:

# 2.3.1 Study Design

We propose over three years to randomize fifteen to twenty patients with refractory depression to one of three treatments in two consecutive weeks of an ECT treatment cycle. Each patient will complete seven study visits. The first visit will be conducted during the dose-charge titration ECT treatment. Following the titration visit, there will be six separate experimental treatments per patient in two blocks of three, with a random sequence in each block (Figure 1). During these six visits, patients will be randomized to receive one of three treatments, all of which are likely to have efficacy in treating refractory depression: 1) ketamine alone, 2) ketamine plus ECT, or 3) standard of care anesthetic plus ECT.

**Figure 1:** Block randomized, repeated measures, crossover experimental design for reconstitution of consciousness and cognition following electroconvulsive therapy (ECT) and general anesthesia. K, ketamine; E, etomidate, Rx, treatment.

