anesthesia will be induced with ketamine, approximately 2 mg/kg, or standard of care. Following bolus of the induction agent, loss of responsiveness and evelash reflex will be confirmed. Loss of consciousness will be recorded as the first time when a subject fails to correctly respond to the command. Care adherent to the ASA guidelines will be performed regardless of treatment session. For sessions with ECT, pre-stimulation hyperventilation and assisted ventilation will also be performed. Central seizure duration will be assessed from bilateral fronto-mastoid EEG by the psychiatry team. Peripheral seizure duration will be determined through monitoring of tonic-clonic activity (Fink and Johnson 1982). During the sessions that subjects receive ECT, other drugs will also be administered according to current practice and as clinically indicated. The return of eye opening will be assessed every 30 seconds and defined for the initial time at which the patient opens his eves to verbal command. The ability to extend the thumb to verbal command ("thumbs up") will be assayed every 30 seconds. Return of responsiveness to auditory command will be defined as the first time at which the patient has squeeze his correct hand the number of times instructed via auditory commands. At this time, defined as t = 0 minutes, the subject will begin a series of cognitive and behavioral assessments, which are repeated every 30 minutes up to two hours after return of responsiveness. Patients will be permitted to take brief breaks to use the restroom and eat or drink, as necessary. At the conclusion of each treatment session, depression testing (PROMIS-CAT) and mood assessment (Self-Assessment Manikin) will be performed to assess for early improvements in mood. To assess blinding quality, the patient will be asked their impression of whether they received ECT that day. They will be discharged according to standard post-anesthesia care unit discharge criteria upon completing the last neurocognitive test battery. A study site coordinator will contact each subject within 24 hours of the study day to assess and document any adverse events.

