### 2.5.2 Primary Analyses:

Recovery of Responsiveness: Given that the induction of generalized seizures by electrical stimulation may compound the recovery from general anesthesia, we expect that interval from loss to return of responsiveness following ketamine + ECT will be longer compared to the period for ketamine + sham ECT. We will determine the median and 95% confidence intervals for this measure in relation to the treatment intervention.

Recovery of Cognition: Given that postictal suppression may be prolonged with ketamine than with etomidate(Hoyer, Kranaster et al. 2014), we hypothesize that the time needed for the return of cognition to baseline on individual sessions will be greatest for ketamine + ECT, followed by etomidate + ECT, and ketamine + sham ECT. Separate mixed-effects models will be generated based on reaction time and accuracy. We will determine the time of convergence for 95% confidence intervals for the marginal responses related to

the three treatment groups. To determine the timing for the recovery to baseline, we will determine the time when the same 95% confidence intervals include 0.

Postictal Delirium and Cognitive Recovery: We expect the incidence of delirium (3D-CAM) to be associated with delayed restoration of baseline function in all cognitive domains. The magnitude and significance of this relationship will be determined from the mixed effects models for each cognitive test.

Comparison of Cognitive Recovery After ECT and Isoflurane General Anesthesia: We hypothesize that the time for recovery to baseline will be quicker for treatments involving ECT compared to that for the recovery from isoflurane general anesthesia. Convergence for 95% confidence intervals will be compared between treatment groups.

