### **Post-treatment:**

Recovery of consciousness (ROC) will be defined as the first time at which subjects correctly responded to two consecutive audio loop commands. At this time, defined as t = 0 minutes, the subject will begin the neurocognitive battery of tests followed by a brief resting period. Neurocognitive testing will be repeated at t= 30, 60, and 90 minutes following emergence while the 3D-CAM will be completed at time 0 and every hour (Table 1) until the patient is scored negative for delirium. Each battery of neurocognitive testing will take

approximately 15-20 minutes to complete. During the rest period, EEG recording will occur with 5 minutes eyes open and 5 minutes eyes closed. At the 90 timepoint patients will not only complete the COGNITION cognitive test but also the 3D-CAM (if positive for delirium at t=60, PROMIS-CAT, Self-Assessment Manikin, and a questionnaire regarding patients' subjectivity of whether they received ECT. Subjects will be permitted to take a brief break to use the restroom and eat or drink, as necessary. Subjects will be discharged according to standard post-anesthesia care unit discharge criteria upon completing the last neurocognitive test battery. A study site coordinator will contact each subject within 24 hours of the study day to document any adverse events.

Assessment	Baseline (Pre-ECT)	Time 0	Time 30	Time 60	Time 90
COGNITION Neurocognitive Testing	х	Х	Х	Х	Х
3D-CAM - Delirium (3D- Confusion Assessment Method)	х	х		х	х
PROMIS-CAT - (Computer Adaptive Testing for depression)	Х				х
Mood Self-Assessment Manikin - mood	Х				х
Scale of Suicidal Ideation	х				
Assessment for Blinding Quality					х

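### The cognition models name random effects only for the participant, although treatment is assigned per session; read literally, session-level contrasts are reported too precisely, by an amount that depends on the unstated time coding and interaction

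*Combined protocol and SAP*

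**What the plan says.** All references are to the combined protocol and SAP.

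- **Model (2.5.1).** The model is described in one sentence: "Time and treatment intervention group will be included as fixed effects while random effects will account for repeated measures provided by each participant". No session term, participant-by-treatment term, residual correlation, treatment-by-time interaction or coding of time is named, there or in 2.5.2. Day of treatment, dose charge, central seizure duration and age enter as covariates.
- **Unit of assignment (2.3.1).** After titration, "there will be six separate experimental treatments per patient in two blocks of three, with a random sequence in each block". Each of the three treatments is therefore given in two sessions per patient.
- **Batteries per session.** A battery is given at return of responsiveness (t = 0). Appendix 1, Post-treatment, then says "Neurocognitive testing will be repeated at t= 30, 60, and 90 minutes following emergence", which agrees with Table 1 and makes four. Section 2.3.8 says testing is "repeated every 30 minutes up to two hours after return of responsiveness", which read literally makes five. These places must be reconciled.
- **Inference (2.5.2).** For cognition, "We will determine the time of convergence for 95% confidence intervals for the marginal responses" of the three treatment groups. Recovery is dated to when those intervals include zero. The association of delirium with cognition is taken from the same models.
- **Baseline (2.3.8).** The battery is repeated before treatment at every session.

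**The concern.** The unit that receives a treatment is the session. The batteries of one session share that day's state and, if scores are changes from that day's baseline, the error of one baseline score. A model with only a participant intercept treats the 2 x 4 = 8 batteries per arm per patient as independent given the patient, although they come from two treated sessions. Any quantity that varies between sessions but not within them is then credited with more information than the design provides.

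This matters because 2.5.2 draws its cognition conclusions from model-based 95% intervals. If the covariance structure is left open, it can also be settled after the data are seen.

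**Working it through.** **The plan's own figure.** The only calculation in the plan is the sample size in 2.6. Four time means give 6 pairs. If alpha is divided by 6 (an inference; the plan does not say so), n = 2(SD/difference)²(z₁ + z₂)².

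- Difference 20, SD 20, power 80%: 2 x 1 x (2.638 + 0.842)² = 24.2, against 24 stated.
- Difference 40, SD 20, power 99%: 2 x 0.25 x (2.638 + 2.326)² = 12.3, against 12 stated.

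The figures are reproduced, but the calculation has no session component and so does not help with this question.

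**Inputs.** Six sessions, two per arm; m = 4 batteries at 0, 30, 60 and 90 minutes (Table 1); 15-20 patients; two-sided 0.05 (2.6). The session share ρ = session variance / (session + residual variance), after removal of the participant effect, is not given. I assume 0.1 to 0.5.

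**Why ρ = 0 is unlikely.** An interval that can include zero at recovery implies a change from baseline, though 2.5.2 does not define the scale. Suppose baseline and follow-up scores have equal error variance σ² and there is no true day effect. Two changes from the same baseline then have covariance σ² and variance 2σ² each, so their correlation is 0.5.

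**Variance ratio.** Set session plus residual variance to 1. Let h be the variance that independent batteries would give to one session's fitted value at the time of interest. The true variance is ρ + (1 − ρ)h, so

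true / reported variance = 1 − ρ + ρ/h, and actual error = 2{1 − Φ(1.96/√ratio)}.

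- Time-averaged effect: h = 1/4, so the ratio is 1 + 3ρ.
- Linear time by treatment: h = 1/4 + (t − 45)²/4500, where 4500 = 2(45² + 15²). This gives h = 0.25 at 45 minutes, 0.30 at 30 and 60, and 0.70 at 0 and 90.
- Categorical time by treatment, one time point: h = 1, so the ratio is 1.
- Slope difference: the ratio is 1 − ρ.

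| Contrast, participant intercept only | ρ = 0.1 | ρ = 0.3 | ρ = 0.5 |
|---|---|---|---|
| Time-averaged: true SE / reported SE | 1.14 | 1.38 | 1.58 |
| Time-averaged: error, formula | 8.6% | 15.5% | 21.5% |
| Time-averaged: error, simulated | 8-10% | 17-18% | 22-24% |
| Linear, 30 or 60 min: formula | 7.8% | 13.3% | 18.3% |
| Linear, 45 min: formula | 8.6% | 15.5% | 21.5% |
| Linear, 30-60 min: simulated | 7-9% | 13-17% | 19-25% |
| Linear, 0 min: formula | 5.5% | 6.5% | 7.5% |
| Categorical, one time point: simulated | 4-7% | 4-7% | 4-7% |
| Slope difference: formula | 3.9% | 1.9% | 0.6% |

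The simulations are null trials with 15 to 20 patients, 2,000 to 4,000 per setting where the run count was recorded. They run slightly above the formula at high ρ because the participant effect absorbs part of the session variance: the estimated residual variance averages about 0.93, not 1, at ρ = 0.5.

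**Further checks.**

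- With a session-within-participant term, simulated error for the time-averaged effect is 4.7-5.4% for ρ of 0.1-0.5. A participant-by-treatment term also restores it (4.4-5.5%).
- Change from session baseline with no true day effect gives 23.5% for the time-averaged effect.
- With five batteries the ratio is 1 + 4ρ, and the formula gives 9.8%, 18.6% and 25.8%.
- Delirium entered as one value per session, assuming 25% of sessions positive, gives 17-18% at ρ = 0.3 and 24-25% at 0.5.

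**The case against.** The strongest reply is that the largest figures belong to a contrast the plan does not use. In an additive time-plus-treatment model the arms stay a constant distance apart, so a time of convergence could not be estimated; 2.5.2 therefore implies arm differences that vary with time. If time is categorical and interacts with treatment, the omitted session variance falls into the residual and a single-time contrast is about right. That stands, and it rules out quoting 9-24% as the error rate of the planned conclusions. It does not remove the problem: dating convergence reads most naturally as continuous time, and the understatement then returns, largest in the middle of the window.

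Other replies also have force:

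- The text speaks of random effects in the plural and excludes nothing. A session or participant-by-treatment term would fit it. This stands; the plan is under-specified, not shown to be wrong.
- Day of treatment, dose charge and seizure duration take up some session variation. They remove systematic effects but not one patient's good or bad day.
- Under the recovery rule, an interval that is too narrow delays the declared recovery time and is not a false positive. This stands.
- The error rates describe arm contrasts. The interval for each arm's marginal mean also carries between-patient variance, so its proportional shortfall is smaller.
- Section 2.5 calls the study exploratory. That lowers the stakes, but intervals remain the planned basis for conclusions.

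A reader might infer that every primary cognition interval is too narrow, with false positives of up to a quarter. The documents do not support that: they give neither ρ, nor the time coding, nor a sentence ruling out a session term.

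**Conclusion.** The concern holds as an under-specification whose literal reading is anti-conservative for session-level contrasts. With a participant intercept only and ρ between 0.1 and 0.5, nominal 5% error is about 9-24% for a time-averaged treatment effect and about 7-25% for arm differences at 30-60 minutes under linear time by treatment. Session-level covariates are similarly exposed. Single-time contrasts under categorical time by treatment stay near nominal, slope contrasts are conservative, and return of responsiveness is unaffected. At ρ = 0 there is no inflation.

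Confidence is moderate. The omission is plain in the text and within-session correlation is likely, but the size rests on an assumed ρ and on modelling choices the plan leaves open.

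**What to change.** In 2.5.1, state:

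1. random intercepts for participant and for session nested within participant, or an equivalent within-session covariance, with small-sample degrees of freedom (Kenward-Roger is one option);
2. a treatment-by-time interaction, which the convergence analysis needs;
3. whether time is categorical or continuous, and in what form;
4. whether the response is the score or its change from that session's baseline.

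Use this model for every cognition interval in 2.5.2, including the delirium association. Reconcile 2.3.8 with Appendix 1 and Table 1 on the last battery, since m enters the calculation.

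The cost is a few sentences and no new data: 15-20 patients with six sessions give 90-120 sessions from which to estimate the session variance. Some intervals will be wider than under the participant-only model.

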#### 2.3.5 Study Involvement

The randomized, crossover design of the study is powerful, as it will allow several within-patient comparisons, which will provide optimal efficiency to address the hypotheses. Specifically, the design will allow us to distinguish between the effect of ketamine anesthesia alone versus the combined effect of ketamine plus ECT. Recovery of consciousness after etomidate is generally rapid. Therefore, the etomidate plus ECT arm should yield additional insights into the contribution of seizures in the form of ECT to impaired consciousness and cognition and provides an additional comparator condition to the ketamine + ECT arm. Intra-patient repetition of each of the three exposures over two weeks will help to establish the reproducible effect of each exposure on the outcomes of interest.

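### Section 2.5.1 brings central seizure duration into the regressions without limiting it to ECT sessions or saying how sham sessions are coded; with sham set to 0, the ketamine + ECT versus sham contrast is no longer the total effect.

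*Combined protocol and SAP*

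**What the plan says.** Section 2.5.1 sets up mixed-effects models: "Time and treatment intervention group will be included as fixed effects". Later in that paragraph comes the covariate sentence, "To address differences in ECT-stimulation responsiveness, regression approaches will account for dose charge, central seizure duration, and age", followed directly by "Models will assess for the effects of treatment on the timing for the return of responsiveness to verbal command and the presence of delirium". The paragraph does not say which models carry duration, to which sessions it applies, or how it is coded or centred.

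Other sections bear on this:
- Section 2.3.8: two of the six experimental sessions are ketamine without ECT stimulation, so they have no induced seizure and no delivered charge.
- Section 2.4.7.1: duration is listed with the secondary EEG outcome measures: "Central seizure duration will be visually determined by clinician evaluation of the frontal-mastoid bipolar EEG ictal complexes".
- Section 2.5.3: seizure length is expected to correlate with the interval from loss to return of responsiveness.
- Section 2.5.2: slower recovery after ECT is expected because "the induction of generalized seizures by electrical stimulation may compound the recovery from general anesthesia".
- Section 2.3.5: "the design will allow us to distinguish between the effect of ketamine anesthesia alone versus the combined effect of ketamine plus ECT".
- Section 2.5.2, cognition readouts: "We will determine the time of convergence for 95% confidence intervals for the marginal responses related to" the three groups, and for return to baseline, "we will determine the time when the same 95% confidence intervals include 0".

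**The concern.** Section 2.3.5 and Aim 2 ask for a total effect: ketamine with ECT against ketamine without it. Seizure duration is a consequence of the randomized treatment and lies on the expected path from ECT to slow recovery. Adjusting for it removes part of what the aim sets out to measure. In the sham arm the variable does not exist, so the fitted contrast depends on a coding choice that the plan does not state.

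The exposed analyses are the cognition mixed models with their CI readouts and the models of responsiveness and delirium announced in section 2.5.1. The responsiveness median with 95% CI in section 2.5.2 names no covariate and is not exposed.

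**Working it through.** The plan gives no figure for a duration-adjusted contrast, so there is none to reproduce.

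**Inputs from the documents.** Two sessions per arm and 15-20 patients (2.3.1). Planning difference 20-40 min and SD 20-40 min (2.6). Seizures under 10 s count as inadequate (2.3.4). Termination within about three minutes, 180 s (background, 2.1.2).

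**Assumed, because the documents are silent.** The slope b of outcome on duration, the mean and SD of duration, and the correlation r between duration and outcome within an ECT arm.

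**1. Sham = 0.** Fit Y = a + tK(ketamine + ECT) + tE(etomidate + ECT) + bD, with D = 0 in sham. Arm indicators reproduce the arm means, so mean sham = a and mean ketamine + ECT = a + tK + b x mean D. Hence

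tK = total effect - b x mean D.

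This holds whether or not b is causal. tK is the effect at zero seizure seconds, which lies outside the data.

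Shift b x mean D, in minutes:

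| Mean duration | b = 0.05 min/s | 0.10 | 0.25 | 0.50 |
|---|---|---|---|---|
| 10 s | 0.5 | 1 | 2.5 | 5 |
| 40 s | 2 | 4 | 10 | 20 |
| 60 s | 3 | 6 | 15 | 30 |
| 180 s | 9 | 18 | 45 | 90 |

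A negative slope reverses the sign and inflates the contrast.

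The same shift without units is r x (mean/SD of duration), in outcome SDs. With r from 0.1 to 0.3 and mean/SD from 2 to 4, it runs from 0.1 x 2 = 0.2 to 0.3 x 4 = 1.2 SD.

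**2. Simulation check.** Random-intercept models, 20 patients, two sessions per arm, true difference 20 min, mean duration 40 s, 100 runs per slope:

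| Slope (min/s) | Contrast without duration | With duration, sham = 0 |
|---|---|---|
| 0 | 19.5 | 19.8 |
| 0.10 | 20.0 | 15.7 |
| 0.25 | 19.4 | 9.7 |
| 0.50 | 20.1 | 0.9 |

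The shift equalled fitted slope x mean duration in every balanced run. With 15% of sessions missing (slope 0.25) it averaged 9.61 against 9.60, with a largest single-run discrepancy of 0.48 min. At zero slope the SE rose from about 3.3 to 6.8 min. In separate runs with mean/SD of duration from 2 to 4, the rise was 1.6 to 2.8 fold. For a logistic delirium model the identity is only approximate.

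**3. Sham missing, rows dropped.** All sham sessions go: 2 x 15 = 30 of 90, or 2 x 20 = 40 of 120. The contrast cannot be estimated, and this failure would be visible.

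**4. Centring.** Centred within each ECT arm with sham = 0, mean D is 0 in every arm and tK is the total effect; simulation agreed. Centring on the pooled ECT mean leaves a shift of b x (ketamine mean - etomidate mean)/2. For example, with means of 60 and 40 s and b = 0.2 min/s, the shift is 0.2 x 20/2 = 2 min. Centring on the mean of all sessions does not remove the shift.

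**5. Marginal responses.** At one common duration D*, the difference is tK + b(D* - D*) = tK, which is shifted. At each arm's own mean it is tK + b x mean D, the total effect.

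**The case against.** The opening clause of the covariate sentence speaks of response to ECT stimulation, which exists only in ECT sessions, and the sentence refers to regression approaches rather than to the mixed models by name. Section 2.3.8 describes seizure duration in the context of ECT sessions, and nothing records a 0 for sham. A missing value would fail visibly, so silent harm needs someone to enter a 0. Section 2.5.3 links duration to return of responsiveness, not to cognitive scores. The minute-scale figures in section 2.6 concern modelled trajectories, whereas the cognition models use reaction time and accuracy, and section 2.5.2 reads out CIs rather than a test of one coefficient. Seizure duration exists in both ECT arms, so comparing anesthetics while accounting for it may be what was intended.

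Most of this stands and limits the point. A reader might infer that the cognition results will be biased, that CI convergence will be declared too early, or that the order of recovery will be reversed. The documents do not support that: they state no sham coding, no slope, no mean duration and no choice of marginal. Such effects are hypothetical.

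Two things survive. The sentence names the covariate in the paragraph defining the treatment models, so an analyst could follow it there in good faith. And an ECT-sessions-only reading still leaves ketamine + ECT versus etomidate + ECT adjusted for a consequence of treatment. That comparison can be informative, but as an association. The exploratory label in section 2.5 does not settle the matter, because section 2.5.2 lists the cognition analyses as primary.

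**Conclusion.** The point holds conditionally and is worth fixing. As written, section 2.5.1 permits a model in which the ketamine + ECT versus sham coefficient is the total effect minus slope x mean duration. The identity is exact in a balanced linear model.

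Its size cannot be fixed from the documents. Over the assumed slopes and durations it runs from 0.5 min to more than the whole 20-40 min planning effect. The rough doubling of the SE at zero slope also belongs to the simulated inputs. The conclusion requires that duration enters the treatment models, that sham is coded 0 and, for the CI readouts, that marginals are held at one common duration. None of these is stated, and none is excluded.

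A smaller point concerns dose charge. The plan's other uses of the term favour the Visit 1 titration value, which is a harmless patient-level covariate. Section 2.4.7.2 also records charge for each treatment, however, and session-level charge would raise the same problem as duration.

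**What to change.** Replace the covariate sentence in section 2.5.1 with two:

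- Models estimating treatment contrasts omit central seizure duration and session-level delivered charge; age and the Visit 1 titration charge may enter as patient-level covariates.
- Duration and delivered charge are used only in secondary models restricted to ECT sessions, reported as associations, including any duration-adjusted comparison of ketamine + ECT with etomidate + ECT.

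The authors should also confirm that dose charge means the titration value. If they prefer to keep duration for precision, it should be centred within each ECT arm, set to 0 for sham, and marginal responses reported at each arm's own mean duration.

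No new data are needed, no sessions are lost, and the seizure-length analysis in section 2.5.3 stays. The cost is the residual variance that duration would explain among ECT sessions: relative to within-arm centring, an SE about 2% larger at an assumed r of 0.2 and about 4% larger at 0.3.
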